Empowering Anxious Parents to Manage Child Avoidance Behaviors: A Randomized Trial of a Single-Session Intervention Targeting Parent Accommodation (Project BRAVE)

Hypotheses, Aims, and Analytic Plan
August 31, 2020

Study Timeline

Recruitment is projected to begin in July 2020 and extend through approximately June 2021.

NOTE: This analytic plan was developed prior to the study's lead authors ([name], [name]) downloading, seeing, or using any of the data collected as part of this trial. Similarly, other exploratory analysis will be pre-registered at a later date under the same conditions.

Study Aims and Hypotheses

The primary goals of the study will be as follows:

1. Examine the SSI's (ORR+Project BRAVE) direct effects on parental accommodation, relative to an information-only control (ORR+delayed SSI) at two weeks follow-up.
2. To assess whether parents' perceive their ability to help their child manage distress as *improved* immediately following the completion of the active SSI (ORR+Project BRAVE), compared to an information-only control (ORR+delayed SSI).
3. Evaluate the SSI's acceptability, per self-report ratings.
4. To assess whether parents' distress tolerance improves in the active SSI (ORR+Project BRAVE) condition versus the information-only control (ORR+delayed SSI) group at two weeks follow-up.

Hypotheses associated with each of these primary aims will be as follows:

1. Parental accommodation of child anxiety will decrease significantly more among parents assigned to the ORR+Project BRAVE group, relative to parents assigned to the ORR+waitlist group from baseline to 2-week follow-up
2. Relative to parents who receive ORR, parents who receive Project BRAVE will be more likely to perceive increases in their preparedness to cope with their child's distress from before to after completing their baseline session.
3. Participants assigned to the Intervention Group will find Project BRAVE to be acceptable, indicated by a mean score of > 3 (out of 5) across Program Feedback Scale items (completed by parents assigned to the intervention group at immediate post-intervention).
4. Parents' self-reported distress tolerance will decrease significantly more among parents in the ORR+Project BRAVE group relative to those ORR+waitlist group from baseline to 2-week follow-up

Sample Size Justification

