Using G*Power 3.1, sample sizes needed to detect group differences in the primary outcome (changes in accommodation from baseline to follow-up) between the BRAVE group and the Control group of small (.2), medium (.5), and large effects (.8) based on an F test, linear multiple

regression with $\alpha = .05$ and power = 0.80 were 395, 55, and 25, respectively for the primary outcome (hypothesis 1). The target sample of 300 (150 per SSI condition accounting for attrition) reflects power to detect a small to medium effect as observed by previous SSI trials.

Analytic Plan

To address *hypothesis 1*, a multiple linear regression with intervention condition (1=ORR+Project Brave; 0=ORR+waitlist control) and baseline accommodation levels (sum score of the first 9 items of the Family accommodation scale with higher scores indicating higher levels of accommodation) as predictor variables will indicate whether ORR+Project BRAVE, versus ORR+delayed SSI access, led to differential reductions in accommodation behavior from baseline to 2-week follow up. A p-value of $<.05$ will indicate a significant change in parental accommodation from baseline to 2-week follow up.

To address *hypothesis 2*, we will use the two-sample t-test to determine whether the difference between the ORR+project BRAVE and ORR+delayed SSI access group's mean ratings of the perceived post intervention condition change item is significant. A p-value of $<.05$ will indicate a significant difference between the two conditions. Descriptive statistics of the scores for both conditions will be reported as well with a mean rating above 3 (out of 5) indicating an overall, subjectively-detectable pre-to-post change.

To address *hypothesis 3*, we will examine mean scores on the Program Feedback Scale from the intervention group only. A score above 3 on any given program feedback scale item will reflect endorsement of that item (e.g. positive feedback/adequate acceptability). Thus, a mean score of 3 or higher (out of 5) across participants in this study will indicate participants found the intervention acceptable.

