To address *hypothesis 4*, a multiple linear regression with intervention condition (1=ORR+Project Brave; 0= ORR+waitlist control) and baseline parental distress in the context of child negative affect as predictor variables will indicate whether ORR+Project BRAVE versus ORR+delayed SSI led to greater reductions in parental distress from baseline to 2-week follow up. Parental distress will be indicated by the sum score of the distress tolerance scale. A p-value of $<.05$ will indicate a significant change in parental distress in the context of child negative affect from baseline to 2-week follow up.

Testing Assumptions

To justify the use of linear regression models for the purpose of prediction, we will check the following principle assumptions: 1) linearity and additivity of the relationship between dependent and independent variables, 2) statistical independence of the errors, 3) homoscedasticity of the errors, 4) normality of the error distribution. Nonlinearity will be tested by checking for a symmetric distribution of points on a plot of observed versus predictive values or residual versus predicted values. To check statistical independence of the errors, residual autocorrelations will be plotted to identify values that fall outside the 95% confidence band around zero. Homoscedasticity will be checked by plotting the residuals versus the predicted

values to examine the distribution of residual scores. Finally, normally distributed errors will be checked via normal probability plot to measure skewness and kurtosis.

Missing Data

We will impute any missing data using the expectation-maximization and bootstrapping algorithm implemented with Amelia II in R after running a sensitivity analysis to ensure that data is not missing at random. These imputed datasets allow for more conservative intent-to-treat analyses than listwise deletion or last-observation carried forward. We plan to impute as many datasets as there are percent of missing data for an outcome – rounding up to the next highest percentage (e.g., If 2.4% of data is missing on an outcome, we will create 3 imputed datasets). This process will allow us to retain high power even in the presence of missing data. Cohen's d effect sizes and 95% confidence intervals for analyses will be calculated using t -values for the treatment effects obtained from the analyses with the MOTE package in R.

False Discovery Rate

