The false discovery rate (FDR) will be applied to identify potential false-positive results. Q -values will be computed for p -values from each mixed effects linear model using an online calculator applying Benjamini and Hochberg's approach Benjamini and Hochberg's approach (1995); www.sdmproject.com/utilities/?show=FDR). Results from tests described above will be considered significant if FDR corrected $q < 0.05$.

Methodological Details Not Mentioned Elsewhere

Follow-up Period

We are intending on a 2 week follow-up period from the SSI but will allow up to 5 weeks post-intervention. Participants will be reminded once every two days for 6 days (total of 3 reminders) to complete the post-intervention questionnaires.

Operational Definition of Completion Rates for participants assigned to both conditions

Intervention completion rates for the ORR+ Project BRAVE group will be treated as a categorical (full completers, psychoeducational content completers, personalized-plan completers).

Categorical definitions of completion rates are defined as follows: full completers are all participants who reached the end of the SSI content (slide Q254), psychoeducational completers are all participants who received all of the psychoeducational content of the program (slide Q235), and personalized-plan completers are all participants who completed the step-by-step action plan for responding in a helpful way to their child's anxiety or avoidance (slide Q243)

Excluding Participants From Analysis

Participants will be excluded from analyses *only* if it is apparent from their free responses during the SSI that they are non-english speakers. If a participant completes either the baseline or

follow-up survey more than once, their *more-complete* response will be used in analysis (if responses are equally-complete, their *first* response will be used).

Differential Dropout Rates

We will assess for differential follow-up rates among full completers in each group by using Z-tests of differential proportions where we compare the proportion of people who drop out before completing the follow-up (Y or N) as a function of treatment condition (1 = ORR+Project Brave; 0 = waitlist control).

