For participants assigned to the ORR+ delayed SSI access group, a participant must have made it through all baseline measures (i.e., they must reach the final “page” of the baseline questionnaires, or the RCADS, though it is acceptable for the participant to leave the answer blank after seeing it) to be considered a “full completer”. For participants assigned to the ORR+Project BRAVE group, a participant must have made it through all of the intervention (i.e. they must reach the final “page” of the intervention) to be considered a full completer.

To be considered a follow-up “completer”, a participant must have made it through all of the questionnaires in the follow-up surveys (i.e. they must reach the final “page” of the follow-up questionnaires though it is acceptable for the participant to leave the answer blank after seeing it).

If the p value is greater than .05 we will assume dropout was not dependent on condition assignment and can proceed with interpreting the effects of intervention assignment. If the p value for this test is less than .05 we will conclude that dropout was dependent on condition assignment, and we will take the following steps to improve the interpretability of our results. Unequal dropout between treatment groups can introduce bias in trial results; however, this is not always the case (Bell, Kenward, Fairclough, & Horton, 2013; <https://doi.org/10.1136/bmj.e8668>). One major concern is that, if data is not missing at random, systematic differences may exist between “dropouts” and “completers” that cannot be corrected for, limiting the interpretability of our results. For example, if more control condition participants experienced a worsening of clinical symptoms and dropped out before completing follow-up measures, this worsening of symptoms would not be captured by completers’ data (or by data imputed based on the available completers’ data). Thus, should unequal dropout exist between conditions in the present study, we will report the results of our main analyses while highlighting (1) limitations to interpretation, and (2) ways in which this will inform future intervention development.

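### The only analysis exclusion is judged from text written during the SSI, so as written it can remove randomised parents from the BRAVE arm but not the same kind of parent from control

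*SAP*

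**What the plan says.** The SAP has one rule for leaving a participant out of the analyses (Excluding Participants From Analysis). It applies solely "if it is apparent from their free responses during the SSI that they are non-english speakers". No parallel source of text and no language check is given for control parents.

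Other sections show who takes the SSI, and when:

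- **Study Aims and Hypotheses, aim 1:** "Examine the SSI's (ORR+Project BRAVE) direct effects on parental accommodation, relative to an information-only control (ORR+delayed SSI) at two weeks follow-up". The SSI is the BRAVE arm's treatment, and the comparator gets information with later access.
- **Analytic Plan, hypothesis 1:** the model is "a multiple linear regression with intervention condition (1=ORR+Project Brave; 0=ORR+waitlist control) and baseline accommodation levels", so the comparator is a waitlist arm.
- **Differential Dropout Rates:** to be a full completer in control, "a participant must have made it through all baseline measures"; in BRAVE, "a participant must have made it through all of the intervention". Control completion involves no SSI content.

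Under Missing Data, the SAP says of its imputation: "These imputed datasets allow for more conservative intent-to-treat analyses than listwise deletion or last-observation carried forward".

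**The concern.** An exclusion made after randomisation is harmless to a between-arm comparison only if it would act alike whichever arm a parent was assigned to. This one cannot, because the material it is judged on exists in one arm only. Suppose two parents with equally little English are randomised, one to each arm. The BRAVE parent may reveal this in the SSI text and be removed. The control parent has written no SSI text and stays.

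The contrasts for hypotheses 1, 2 and 4 could then set a BRAVE arm screened for such parents against an unscreened control arm. If these parents' outcomes differ after baseline adjustment, part of that difference would appear as an intervention effect. Hypothesis 3 uses the intervention group only, so no between-arm comparison is affected there.

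The judgement also cannot be blind, since anyone reading SSI text knows the arm, and the SAP gives no criterion for when poor English counts as apparent.

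**Working it through.** **Step 1: does the rule act on one arm only?** The trigger is free text given during the SSI. The aims and the primary model describe control as information-only and waitlist, and control completion is defined by baseline questionnaires. Up to the immediate post-session rating (hypothesis 2) and the 2-week follow-up (hypotheses 1 and 4), only BRAVE parents can supply that text. The rule is worded as the sole ground for exclusion, so no other analysis rule removes matching controls.

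**Step 2: does another part of the SAP repair it?**

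- Imputation (Missing Data) fills in missing values. An excluded parent is outside the analysis, not a missing value.
- The dropout Z-test compares failure to complete follow-up among full completers. It does not count exclusions.
- The 25th/75th percentile sensitivity analysis covers dropouts and missing data, and runs only if dropout is unequal.

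None of the three addresses the rule.

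**Step 3: how large could the effect be?** The SAP states no figure for this, so there is none to reproduce.

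Input from the SAP: 150 per arm (Sample Size Justification), two-sided α = .05.

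Assumed inputs: p, the share of such parents in each arm; g, their shift on the outcome in SD, adjusted for baseline; residual SD 1; every such BRAVE parent is detected; every such control parent is observed.

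Formulas:

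- Expected BRAVE exclusions = 150p. Comparable control exclusions = 0.
- The control mean shifts by p × g and the screened BRAVE mean by 0, so |bias| = p × g.
- SE = √(1/150 + 1/[150(1 − p)]).
- False-positive rate = Φ(−1.96 − bias/SE) + 1 − Φ(1.96 − bias/SE).

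Worked example, p = 5% and g = 1.0: bias = 0.05 × 1.0 = 0.05; SE = √(1/150 + 1/142.5) = 0.117; bias/SE = 0.427; rate = 7.1%.

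| p | g (SD) | BRAVE parents removed | Bias (SD) | False-positive rate |
|---|---|---|---|---|
| 1% | 0.5 | 1.5 | 0.005 | 5.0% |
| 2% | 0.5 | 3 | 0.010 | 5.1% |
| 2% | 1.0 | 3 | 0.020 | 5.3% |
| 5% | 0.5 | 7.5 | 0.025 | 5.5% |
| 5% | 1.0 | 7.5 | 0.050 | 7.1% |
| 10% | 1.0 | 15 | 0.100 | 13.4% |

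A simulation of the same set-up (40,000 trials per setting, no true effect) gave 5.0%, 5.2%, 5.2%, 5.5%, 7.1% and 12.9% in the same order, with mean biases within 0.001 SD of p × g.

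**Step 4: what if the matching controls are partly lost?** If half of them give no follow-up and simply leave the comparison, their share among the remaining controls is 0.5p/(1 − 0.5p). For p = 5% this is 0.025/0.975 = 0.026, and for p = 10% it is 0.05/0.95 = 0.053. With g = 1.0 the rates fall to about 5.5% and 7%. The SAP would impute these controls rather than drop them, and that is not modelled here.

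**The case against.** The strongest reply concerns size, and most of it stands. The SAP gives no share of non-English speakers and no outcome difference, so every rate above rests on assumption. If the share is 1-2% with a half-SD shift, the error rate is essentially nominal. The protocol, which is not shown, may require English at enrolment. That would act on both arms and could bring p close to zero. The calculation is near worst case: full detection in BRAVE, full follow-up in control, and 150 analysed per arm although the SAP says that number allows for attrition. It also uses the raw p < .05, whereas the SAP's final criterion is a false discovery rate q < 0.05.

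A reader might infer that the rule favours BRAVE, or that it invalidates the primary comparison. The documents support neither. Nothing in the SAP says that parents who struggle with English items do worse after baseline adjustment. Their answers could be shifted either way or be mostly noise. Nor does any figure in the SAP show that many parents would be excluded.

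The intent-to-treat conflict should not be pressed far either. The SAP uses the term when comparing imputation with listwise deletion and last observation carried forward, not to define an analysis population. There is tension, but it adds little to the asymmetry itself.

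Two other replies do not stand. Controls might later write SSI text through delayed access, but the SAP neither dates that access nor says the text would be used. Only those who took it up could be screened, so the rule would still be unequal. The sample-size section does apply the phrase SSI condition to both arms, but the aims and completion definitions show that this is loose wording.

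**Conclusion.** The rule is wrong as written. It is a post-randomisation exclusion that can operate in one arm only, it bears on hypotheses 1, 2 and 4, and no other provision of the SAP offsets it. That conclusion follows from the text and needs no assumed value.

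The consequence is uncertain in size and sign. It runs from nothing noticeable when one to three BRAVE parents are removed to a bias of 0.10 SD when fifteen are removed and their outcomes differ by a full SD. That upper end is half of the .2 the SAP labels a small effect. These sizes rest on the assumed p and g, full detection, full follow-up and 150 analysed per arm. The point is one that should be fixed; a claim of serious bias would need figures that the SAP does not contain.

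**What to change.** Replace the exclusion rule with a statement that all randomised parents are analysed in the arm assigned and that nobody is excluded because of responses given during the SSI.

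If a language exclusion is wanted, define it only on information collected from both arms before assignment, such as baseline responses. Give an explicit criterion and have it applied by someone who does not know the arm. The exclusion based on SSI text can be kept as a labelled sensitivity analysis, with the number removed reported.

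The cost is a change of wording, with no new data for the main rule. The downside is that a few parents who could not use the English programme stay in the BRAVE arm and may dilute the estimate slightly.

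### The duplicate rule lets a later, fuller baseline record replace the first, so a post-exposure value can become the covariate for hypotheses 1 and 4 (small effect, cheap to fix)

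*SAP*

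**What the plan says.** The rule is in the SAP under Excluding Participants From Analysis. It covers both surveys: "If a participant completes either the baseline or" the follow-up survey "more than once, their *more-complete* response will be used in analysis". Order matters only for ties: "if responses are equally-complete, their *first* response will be used". The rule does not say how completeness is measured. It does not require the kept baseline to come before assignment or exposure, and it does not say which arm applies if two records differ.

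Three other places bear on it:

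- **Analytic Plan.** The models for hypotheses 1 and 4 regress on intervention condition and the baseline value of the outcome, so the kept baseline enters both as a covariate.
- **Differential Dropout Rates.** A full completer is defined differently by arm. For controls: "For participants assigned to the ORR+ delayed SSI access group, a participant must have made it through all baseline measures". For BRAVE: "a participant must have made it through all of the intervention". The control definition allows for a parent who has been assigned but has not finished baseline.
- **Missing Data.** Any missing data are to be imputed, and the imputed datasets are said to "allow for more conservative intent-to-treat analyses" than the alternatives named there.

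**The concern.** A baseline covariate should be measured before anything the arm could affect. A repeat baseline is by definition later than the first entry, so it may follow assignment and may follow exposure to BRAVE or ORR. Where the first record is incomplete and the second is fuller, the rule prefers the second. If the intervention has already moved that second answer, adjusting for it removes part of the effect that the model is meant to estimate.

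There is also a conditional route. If a second entry were randomised again, choosing a record by completeness could mean choosing an arm by what the parent did after the first assignment. The SAP is silent on re-randomisation, so this is a possibility to close off and not a described feature of the trial.

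**Working it through.** **The plan's own figures.** The SAP gives no number for duplicates. Its only computed figures are the sample sizes 395, 55 and 25 (Sample Size Justification). A noncentral F test of one predictor at alpha .05 and power .80 returns exactly these for f² = .02, .15 and .35. They do not bear on this point, except that the same method at N = 300 gives a smallest detectable f² of 0.02633, or d = 2 × √0.02633 = 0.325 for equal arms. That value is used below as an illustrative effect.

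**Inputs.** From the SAP: N = 300, 150 per arm, regression on arm and baseline. Assumed: baseline slope 0.6 on standardised scores; the share p of BRAVE parents whose kept baseline is post-exposure; and the shift s in that baseline caused by the exposure.

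**Step 1: bias from a post-exposure covariate.** If a share p of the BRAVE arm has its baseline lowered by s, the arm's mean baseline falls by p × s, and the adjusted effect shrinks by slope × p × s. If repeating controls also shift after ORR, the quantity is slope × (p × s in BRAVE minus p × s in control), which is smaller.

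With p = .05 and s = .325: 0.6 × .05 × .325 = 0.010 SD. This supposes that the repeat baseline already shows the whole effect.

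**Step 2: simulation check.** 4,000 replicates, N = 300, true effect −0.30, s = 0.30, 5% of controls repeating with no shift:

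| p in BRAVE | slope × p × s | estimate, kept baseline | estimate, first baseline | power, kept vs first |
|---|---|---|---|---|
| 5% | 0.009 | −0.291 | −0.300 | 0.87 vs 0.89 |
| 10% | 0.018 | −0.281 | −0.299 | 0.86 vs 0.89 |
| 20% | 0.036 | −0.264 | −0.300 | 0.80 vs 0.90 |

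The formula and the simulation agree.

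**Step 3: scale.** With slope 0.6 taken as the correlation, the residual SD is √(1 − 0.36) = 0.8 and the standard error of the effect is 0.8 × 2/√300 = 0.092 SD. A bias of 0.010 is about one-ninth of that.

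**Step 4: the conditional arm route, only if repeat entry re-randomises.** Suppose a share k of 150 BRAVE parents re-enter, half are moved to control, and they differ from the rest by δ at follow-up. The shift is mδ/(150 − m) + mδ/(150 + m), with m = 150 × k × 0.5.

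- k = .03, δ = .3: m = 2.25; 0.675/147.75 + 0.675/152.25 = 0.009 SD.
- k = .10, δ = .5: m = 7.5; 3.75/142.5 + 3.75/157.5 = 0.050 SD.

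This is a high-side figure: all movement is one way and baseline adjustment is ignored. A simulation with the adjusted model, no true effect, and less motivated parents (who also do worse) leaving BRAVE unfinished gave estimates of about 0.00, −0.01, −0.02 and −0.03 SD at 2%, 5%, 10% and 20% repeaters, with type I error of at most about 0.06. In this scenario the error favours BRAVE.

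**The case against.** The strongest reply is that the mechanism is narrow and the consequence slight. Four parts of it stand.

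- **The tie-break protects most cases.** If the baseline questionnaires precede the intervention content (the order is not stated), a BRAVE parent who has seen the content will normally have passed through them already. A repeat then ties and the first is kept. A later baseline wins only where the first had blanks or an early exit, or if completeness counts intervention pages, which the SAP does not say.
- **The unfinished-baseline wording concerns controls only.** It does not show a BRAVE parent with an unfinished baseline who has seen BRAVE content. A reader might also infer that the longer BRAVE session leaves more incomplete first records; that is plausible but undocumented.
- **Intent-to-treat is not breached in general.** A reader might infer that the rule contradicts the intent-to-treat aim whether or not anyone is reallocated. It does not: if each parent stays in the assigned arm, a late covariate attenuates the estimate but leaves the allocation intact. The sentence under Missing Data compares imputation with other ways of handling missing values and says nothing about duplicates.
- **Arm switching is not described.** The SAP speaks throughout of assigned groups, and how repeat entries are linked or blocked is a matter usually left to the protocol, which is not at hand.

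What the reply does not remove is that the rule, as written, places no timing condition on the kept baseline. Blank items are the very case in which completeness overrides order, and the plan already has a way of handling blanks.

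**Conclusion.** The point holds as a low-severity improvement. The rule permits a post-exposure baseline to replace an incomplete earlier one in the models for hypotheses 1 and 4, with a likely bias towards the null of about 0.01 SD at 5% affected BRAVE parents and about 0.04 SD at 20%. These sizes rest on an assumed slope of 0.6 and a shift of about 0.3 SD. The share affected is unknown, and it is smaller than the share of repeat entrants because ties keep the first record. The arm consequence depends wholly on re-randomisation that the SAP does not mention, so it should be put as a question to the sponsor. The documents do not support a finding that allocation is broken, or that the handling of repeated follow-up surveys needs to change.

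**What to change.** Amend the duplicate rule for baseline only: analyse every participant in the originally assigned arm and use the first baseline record. Completeness may choose only among baseline records all made before any assignment or exposure; a later record never replaces an earlier one. Fill blank baseline items through the imputation already planned. Report the number of repeat entrants by arm, so that readers can judge whether the issue arose.

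Leave the follow-up duplicate rule as it is. No problem with it has been shown, and choosing follow-up records by the accommodation score alone could discard a record that holds the distress-tolerance outcome for hypothesis 4.

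The cost is a short change to the text, one extra line of reporting, and a few more imputed baseline items, including some for controls whose later answers followed ORR alone.

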Further, if unequal dropout is present, we will run a sensitivity analysis to determine a range of possible effect sizes for our outcomes of interest, varying how much “dropout participants” may have changed on each outcome. To establish lower- and upper-end estimates of effect size, we will: (1) calculate residual change for each of our 3 outcomes, (2) identify the 25th and 75th percentile values for residual change in each outcome, (3) run analyses for each outcome where we impute the lower residual change value (25th percentile) for all dropouts/missing data, as well as the higher residual change value (75th percentile) for all dropouts/missing data. This approach explicitly assumes data are not missing at random, providing a more unbiased estimate of the overall treatment effect in the presence of unequal dropout.

Exploratory Moderation Tests

We will also conduct exploratory moderation tests examining various baseline variables as moderators of the SSI's impact on outcome, using the same approaches to missing data and corrections for multiple tests as described elsewhere in the pre-registration

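### The differential-dropout test counts BRAVE parents only from the end of the intervention but control parents from the end of baseline, so it cannot see loss among BRAVE parents who leave the session

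*SAP*

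**What the plan says.** The section Differential Dropout Rates sets the test: "We will assess for differential follow-up rates among full completers in each group by using Z-tests of differential proportions". The event is failure to complete follow-up, compared by arm.

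The same section defines the population separately for each arm. In the delayed-access control, "a participant must have made it through all baseline measures". In the active arm, "For participants assigned to the ORR+Project BRAVE group, a participant must have made it through all of the intervention". The section on completion rates agrees on the active arm: "full completers are all participants who reached the end of the SSI content".

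The result decides what follows. "If the p value is greater than .05 we will assume dropout was not dependent on condition assignment", and the effects are then interpreted. If p is below .05, limitations are highlighted and a further analysis is added: "Further, if unequal dropout is present, we will run a sensitivity analysis to determine a range of possible effect sizes". That analysis gives all missing outcomes the 25th and then the 75th percentile of residual change.

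The Missing Data section describes the main analysis: "These imputed datasets allow for more conservative intent-to-treat analyses than listwise deletion". The only exclusion from analysis is for parents where it is "apparent from their free responses during the SSI that they are non-english speakers".

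**The concern.** The two arms enter the test at different points. Reaching the last baseline page requires nothing of the intervention. Reaching the last intervention page is a post-randomisation event that depends on engagement with the intervention itself. A BRAVE parent who finishes baseline and then leaves the session is in neither the numerator nor the denominator, and controls face no corresponding filter after baseline.

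Those parents still belong to the intent-to-treat population, and if they do not return their outcomes are imputed. So the test examines a different population from the one analysed, and the parents it omits may well be the least likely to return. The completion categories record how far BRAVE parents got, but they feed neither the test nor its trigger.

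At stake is whether the primary result is reported with limitations and with a range for informative dropout. The SAP itself warns in this section that imputation from available completers would not capture such dropout.

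A smaller related asymmetry: the language exclusion relies on free text given during the session, which BRAVE parents have more opportunity to provide than delayed-access controls. No size can be put on this from the document.

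**Working it through.** **Inputs.** From the SAP: 150 per arm (Sample Size Justification), the two definitions of full completer, and the .05 threshold. The SAP gives no dropout figure to reproduce. Assumed for illustration: every control parent reaches the last baseline page; 30 of 150 BRAVE parents (20%) quit the session; loss to follow-up is equal among BRAVE full completers and controls (20%, varied to 10% and 30%); the share of quitters lost varies.

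**Formula.** Pooled two-sided test: z = (x₁/n₁ − x₂/n₂) / √[p(1−p)(1/n₁ + 1/n₂)], with p = (x₁+x₂)/(n₁+n₂).

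**Planned test.** BRAVE full completers number 150 − 30 = 120, of whom 20% (24) are lost; controls lose 30 of 150. Then z = (0.20 − 0.20)/0.049 = 0 and p = 1.00. The quitters do not appear in this expression, so their fate cannot alter it.

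**All randomised, same data.** BRAVE losses are 24 plus the quitters lost.

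| Quitters lost | BRAVE | Control | z | p |
|---|---|---|---|---|
| 6 of 30 (20%) | 30/150 | 30/150 | 0 | 1.00 |
| 15 of 30 (50%) | 39/150 | 30/150 | 1.23 | .22 |
| 20 of 30 (67%) | 44/150 | 30/150 | 1.87 | .061 |
| 21 of 30 (70%) | 45/150 | 30/150 | 2.00 | .046 |
| 30 of 30 (100%) | 54/150 | 30/150 | 3.09 | .002 |

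For the 21-of-30 row: p = 75/300 = 0.25, the standard error is √(0.25 × 0.75 × 2/150) = 0.050, and z = 0.10/0.050 = 2.00.

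**Tipping point at other loss rates, 30 quitters.**
- 10% loss elsewhere: 12 + 15 = 27/150 v 15/150, z = 2.00, p = .046, so 15 of 30 (50%).
- 30% loss elsewhere: 36 + 26 = 62/150 v 45/150, z = 2.05, p = .041, so 26 of 30 (87%).

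**Other quit rates, 20% loss elsewhere.** The planned test gives p = 1.00 throughout.
- 10% quit (15): all lost gives 27 + 15 = 42/150 v 30/150, p = .10. The decision does not change.
- 40% quit (60): half lost gives 18 + 30 = 48/150 v 30/150, p = .018.

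**Errors in the other direction.**
- If BRAVE full completers lose 10%, controls lose 20% and all 30 quitters are lost, the planned test compares 12/120 with 30/150 (z = −2.25, p = .024, more loss in control). Among all randomised it is 42/150 (28%) v 30/150 (20%), p = .10, with the observed excess in BRAVE.
- With equal overall loss of 48/150 in each arm, 24 of the BRAVE losses being quitters, the planned test compares 24/120 with 48/150 and gives p = .027.

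**Strength of a non-significant result on the common denominator.** Power ≈ Φ[(d − 1.96·s₀)/s₁], where d is the difference, s₀ the pooled and s₁ the unpooled standard error. At 150 per arm it is 52% for 30% v 20% and 23% for 26% v 20%.

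**The case against.** The test is openly restricted to full completers, and the gate does not touch the primary estimate. Leavers remain in the imputed analysis, their progress is categorised, and nothing forbids reporting overall loss. All of that stands and limits the severity.

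The impact also depends on a quit rate that the SAP does not give. At 10% quitting with every quitter lost, the all-randomised test stays above .05 with 20% loss elsewhere (p = .10) and 30% (p ≈ .20), and crosses only when loss elsewhere is low (10%: p ≈ .03). At 5% quitting, no loss rate from 10% to 40% crosses. If quitters return as often as everyone else, the two tests agree. This stands: over part of the plausible range the decision is the same.

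The reversed-direction example still triggers the caveats and the sensitivity analysis, whereas an all-randomised test at p = .10 would not. That too is fair. The example shows that the test can misdescribe which arm loses more, not that the plan is always less cautious. It is also a reason not to gate on any p-value.

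Finally, the Missing Data section mentions a sensitivity analysis before imputation. It gives no method, so the percentile analysis remains the only specified one that allows for data not missing at random.

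None of this answers the structural point: a test that leaves out one arm's early leavers cannot support a conclusion about dropout by assigned condition.

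**Conclusion.** The concern holds. The definitions alone establish that the planned test cannot register loss among BRAVE parents who leave the session, and that a non-significant result then switches off the limitations and the percentile analysis.

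The size is conditional. With 20% of BRAVE parents quitting, and equal loss among BRAVE full completers and controls, the denominator alone changes the decision once 50%, 70% or 87% of quitters are lost, for 10%, 20% or 30% loss elsewhere. At 10% quitting or below it seldom changes. These figures assume that all control parents reach the last baseline page. The test can also raise a false alarm. Even with the right denominator, power of 23% to 52% for differences of 6 to 10 percentage points makes p > .05 weak ground for assuming independence.

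This should be fixed: it bears on the reporting and robustness of the primary result, not on its value. The language exclusion is a minor addition.

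**What to change.** - Compare follow-up completion by arm among all randomised parents, or among all who reach one milestone common to both arms, such as the last baseline page.
- Report session non-completion in BRAVE and the full-completer comparison descriptively.
- Run the 25th/75th-percentile analysis and state the limitations whatever the p-value, and remove the rule that treats p > .05 as showing independence.
- Base the language exclusion on information collected the same way in both arms, or keep all randomised parents.

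The cost is SAP wording and one routine analysis that is already specified. No new data and no change to the outcome models are needed for the dropout changes. The reported difference in dropout may look less favourable.
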